#### **2.4 OBJECTIVES AND ENDPOINTS**

**Table 2.** Objectives and Endpoints

Objectives	Endpoints				
Primary					
To evaluate the analgesic effects of morphine, fluvoxamine and the two	
 
Pressure Pain: Pain Detection Threshold (PDT), Pain Tolerance Threshold (PTT), Area Under the Curve (AUC), post-test Visual Analogue Scale (VAS)
 
				
drugs as combination using PainCart	
 
Heat pain (pre-cold pressor: unexposed/normal and capsaicin-exposed skin) (only for eligible subjects): PDT, and post-test VAS
 
				
	

Cold Pressor: PDT, PTT, Area Above the Curve (AAC), post-test VAS

				
	4. Electrical Stair test: PDT, PTT, AUC, post-test VAS				
	5. Electrical burst test: PDT, PTT, AUC, post-test VAS				
	

Conditioned Pain Modulation (CPM) Response (change from heat pain pre- and post-cold pressor): PDT

				
	
 
Short Form McGill Pain Questionnaire (SFMPQ) for pressure pain, heat pain, cold pressor, electrical stair test and electrical burst test
 
				
Secondary					
To evaluate the drug- sensitive central nervous system (CNS) functioning of morphine, fluvoxamine and the two drugs as combination by biomarker profiling and the NeuroCart  The evaluate the drug- sensitive central nervous system (CNS) functioning of morphine, fluvoxamine and the two drugs as combination by biomarker profiling and the NeuroCart  The evaluate the drug- sensitive central nervous system (CNS) functioning of morphine, fluvoxamine and the two drugs as combination by biomarker profiling and the NeuroCart  The evaluate the drug- sensitive central nervous system (CNS) functioning of morphine, fluvoxamine and the two drugs as combination by biomarker profiling and the NeuroCart  The evaluate the drug- sensitive central nervous system (CNS) functioning of morphine, fluvoxamine and the two drugs as combination by biomarker profiling and the NeuroCart  The evaluate the evaluation of the evaluat	
 
Body sway:         
 
antero-posterior sway (mm)
 
 
 
Visual Analog Scales (VAS) according to Bond and Lader to assess:         
 
mood (mm),
 
alertness (mm), and
 
calmness (mm)
 
 
 
Visual Analog Scales (VAS) according to Bowdle to assess:         
 
Feeling high (mm)
 
Internal perception (mm)
 
 
 
External perception (mm)
 
N-back
 
 
Average reaction time (ms) (zero-, one-, two-back)
 
Number of correct targets (zero-, one-, two-back)
 
Number of faulty non-target responses (zero-, one-, two-back)
 
 
Saccadic Eye Movement
 
				

	Peak velocity (degrees/sec)				
	o Inaccuracy (%)				
	6. Smooth pursuit				
	
 
Smooth pursuit (%)
 
				
	7. Pupillometry				
	Left and right, pupil/iris ratio				
	8. Adaptive Tracking				
	Average performance (%)				
	9. Visual Verbal Learning Test (VVLT) memory testing				
	o Immediate recall trial 3 (number correct)				
	
 
Delayed recall (number correct)
 
				
	
 
Delayed recognition (number correct)
 
				
	
 
Delayed recognition (reaction time correct) (msec)
 
				
	10. Electroence phalography				
	
 
Frequency ranges for spectral analysis, Delta,
 
Theta, Alpha, Beta, Gamma
 
				
	11.Simple Reaction Time Task (SRT)				
	Reaction time (ms)				
	Questionnaires:				
	12.State-Trait Anxiety Inventory (STAI)				
	
 
State anxiety score
 
				
	13.Brief Symptom Inventory (BSI)				
	
 
General somatic symptoms
 
				
	
 
Cognitive symptoms
 
				
	
 
Interpersonal sensitivity
 
				
	
 
Depressed mood
 
				
	o Anxiety				
	

Hostility

				
	

Phobic anxiety

				
	

Paranoid thoughts

				
	

Psychoticism

				
	

Global severity index

				
To evaluate the blood pharmacokinetic parameters of morphine, fluvoxamine and the two drugs as combination	PK parameters of morphine (and metabolite morphine-6-glucuronide), fluvoxamine by noncompartmental analysis of the plasma concentration-time data: AUCinf, AUClast, CL(/F), Cmax, t1/2, tlag, tmax, Vz(/F)				
To evaluate the safety and	Treatment-emergent (serious) adverse events				
tolerability of morphine,	((S)AEs) throughout the study at every study visit				
fluvoxamine and the two drugs as combination	Concomitant medication throughout the study at every study visit				

Baseline for PD measurements is defined as the **average** value prior to dosing in the morning of Day 1 for each treatment period.

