- Follow up (FU) visit after last treatment.
- Only weight will be measured at FU or upon early termination
- Physical examination at screening includes assessment of the Fitzpatrick skin type and evaluation of acne, freckles, tattoos or scarring on the back.
- A symptoms based physical examination will be performed.
- For women of childbearing potential: Urine beta HCG will be performed either during screening, on the first day of each treatment period or the day before the first day of each
- Treatment Period at discretion of Investigator. In either case, the results must be negative prior to dosing study participants.

  Vital signs will be measured in supine position. Oxygen saturation will be monitored after dosing at 2h until the end of study day 1 of each treatment period.
- Lunch at 0.5h and dinner 8h post dose, snack at 4.5h, time points are indicative. Light breakfast on Day 1 is shortly after wake activity around -3.5hours, after breakfast the subject starts fasting until after dosing. No meal restrictions on day -1 and day 2.
- PK sample taken 3 minutes after dosing
- Capsaicin application at screening must be performed on or before Day -5 to ensure sufficient washout between the capsaicin that is applied at screening and applied on Day 1.
- Capsaicin application will only be performed after enrolment in subjects not allergic or intolerable to the capsaicin solution, as determined at screening
- Sequence of assessments is NeuroCart® before PainCart®, for specific order of assessments see section 6.4.

  Capsaicin heat pain test (and heat pain test on control skin on volar forearm) will only be performed on subjects not allergic or intolerable to the capsaicin solution. Capsaicin heat pain task only applicable for Day 1.

  PainCart® training up to 42 days before dosing and NeuroCart® training up to 21 days before dosing.
- PainCart® and NeuroCart® will be done twice for baseline measurement
- NeuroCart® round with pEEG measurement only in second baseline measurement
- VVLT at 2u post dose will be measured is the immediate recall. VVLT at 5u post dose will be the delayed recall and recognition.
- Discharge time is approximate and only when deemed safe.

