#### 2.2.2 Clinical information

#### Clinical pharmacology

#### Nortriptyline

Nortriptyline is a tricyclic antidepressant (TCA) that is widely used in the treatment of neuropathic pain. Its analgesic effects are primarily mediated through potent inhibition of norepinephrine reuptake and modest inhibition of serotonin reuptake, which enhances descending inhibitory pain pathways in the spinal cord and brain. Nortriptyline also acts as an antagonist at muscarinic cholinergic, histamine H1, and alpha-1 adrenergic receptors, contributing to both its therapeutic effects and side effects profile. Although nortriptyline does not bind directly to opioid receptors, preclinical and clinical studies support its use in combination with opioids like morphine, potentially offering additive or synergistic analgesia. Its pharmacokinetics involve extensive hepatic metabolism, primarily by CYP2D6, with a typical elimination half-life of 18–44 hours, supporting once-daily dosing.

In addition to its reuptake inhibition, nortriptyline antagonizes muscarinic cholinergic, histamine H1, and alpha-1 adrenergic receptors, which contributes to both its analgesic efficacy and side effect profile, including sedation and anticholinergic effects. It does not act on opioid receptors and does not have known activity at the sigma-1 receptor.

Nortriptyline is rapidly absorbed after oral administration and undergoes extensive first-pass hepatic metabolism, primarily via cytochrome P450 2D6 (CYP2D6).25b The absolute bioavailability is approximately 45-60%, with peak plasma concentrations occurring within 2 to 8 hours.

The exact mechanisms by which nortriptyline exerts its analgesic effects are not yet fully understood. However, its ability to modulate serotonin and other neurotransmitters involved in pain processing suggest a multifaceted approach to pain relief.

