#### Clinical pharmacokinetics and metabolism

#### Nortriptyline

Nortriptyline is approximately 92% bound to plasma proteins and has a large volume of distribution (20–40 L/kg), indicating wide tissue distribution. It exhibits a half-life of 18 to 44 hours depending on metabolic phenotype (extensive vs. poor metabolizers). 25a,25b

Metabolism occurs primarily through demethylation to E-10-hydroxynortriptyline and Z-10-hydroxynortriptyline. These hydroxylated metabolites are less active but may contribute modestly to the therapeutic effect. The drug and its metabolites are primarily excreted renally.25b

Nortriptyline exhibits linear pharmacokinetics within the therapeutic range. Steady-state concentrations are typically achieved within 4 to 5 days, and dosing is often titrated slowly to mitigate side effects, especially in older adults.25b

Nortriptyline does not act on opioid receptors. Instead, it is a potent norepinephrine reuptake inhibitor with secondary serotonin reuptake inhibition. 6a,7 Its analgesic effects stem from enhancement of descending inhibitory pain pathways and receptor antagonism at cholinergic, histamine, and adrenergic receptors. 

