#### Treatment and observation period

The overview of all assessments including time schedule is provided in the study flow chart (Table 1). Subjects will present to the CRU in the afternoon of Day -1 (i.e., the day before the study treatment administration) for baseline procedures conducted prior to dosing. Baseline procedures will be performed prior to dosing and study procedures after dosing. Subjects will be discharged in the afternoon of Day 2, approximately 24 hours post-dose.

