#### Nortriptyline

Given its long half-life (18–44 hours), a single morning dose is expected to maintain pharmacologically active plasma levels throughout the assessment period. This supports the choice of 75 mg nortriptyline as an appropriate comparator in this crossover trial.

A previous study in healthy volunteers found that nortriptyline exhibits dose-proportional pharmacokinetics25b. Reported plasma exposure metrics (Cmax and AUC) at single doses are shown below:

Dose (mg)	Cmax (ng/mL)	AUC (ng·h/mL)
25	15	450
50	30	900
75	45	1350

[figure not shown]
A 75 mg oral dose is predicted to yield a peak concentration of approximately 45 ng/mL and an AUC of about 1350 ng·h/mL. This exposure lies below the therapeutic plasma range for *antidepressant* efficacy (50–150 ng/mL), but is expected to provide sustained CNS effects relevant for this trial's pharmacodynamic endpoints.25c Insomnia and dry mouth are the most common dose-limiting side effects at higher doses.

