## 2.10.4 Sequence of assessments and time windows

When the following assessments are scheduled to be performed at the same time-point, the order (of priority) will be as follows: ECG, vital signs, blood sampling for safety, NeuroCart® (pEEG (at applicable timepoints), Saccadic eye movement, Smooth pursuit eye movement, Pupillometry, Adaptive tracking, Bond & Lader, Bowdle, N-Back, VVLT, Body Sway, STAI), PainCart® (Heat pain (pre-cold pressor: unexposed/normal and Capsaicin-exposed skin) Pressure Pain test, Electrical Burst test, Electrical Stair test, heat pain test on unexposed/normal skin Cold pressor pain test, heat pain on unexposed/normal skin test), BSI and physical examination. When a PK assessment is scheduled for the same nominal time as another scheduled assessment, the blood sampling will take precedence.

The deviations of actual time points from the expected time points will be within ten percent, calculated from the zero point, time of drug administration. The expected timepoints are defined as the timepoints in Promasys. Deviations of more than 10% will be explained in a note. These time deviations only apply for ECG, vital signs, blood sampling for PK, first test of a NeuroCart® round, and first test of a PainCart® round.

Pre-dose assessments are given in indicative expected times.

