### Analysis of pharmacokinetic endpoints

The individual plasma nortriptyline, morphine, and M6G concentrations will be listed by treatment, subject, visit and time. Individual plasma drug concentrations versus time will be plotted in panel plots for each treatment using both a linear and log y-axis.

The individual plasma morphine and nortriptyline concentrations will be summarised (number of samples [n], mean, standard deviation [SD], % coefficient of variation [CV], median, minimum [Min] and maximum [Max] values) by treatment and time, and will also be presented graphically as mean over time, with standard deviation as error bars.

When an actual sampling time of a drug concentration sample differs from the protocol time by more than 10% and at least 5 minutes, the concentration will be excluded from calculation of descriptive statistics and a note will be added to the sample in the listing. A sample will in general not be excluded from the non-compartmental analysis due to deviation from the protocol sampling times.

The individual PK parameters (except tmax and tlag) will be summarized (n, mean, SD, %CV, geometric mean, geometric %CV, median, Min and Max) per treatment group and will be presented graphically as boxplots. For tmax and tlag, the n, median, Min and Max statistics will be reported. The procedure for non-compartmental analysis at CHDR including the post and pre-processing of data is described in SOP SDANCA.

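### The terminal-phase noncompartmental PK parameters for nortriptyline, and the terminal and per-dose parameters for morphine, are not reliably estimable from the Table 1 sampling schedule

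*Protocol*

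**What the plan says.** Section 2.4, Table 2, lists the PK endpoints for morphine, its metabolite M6G and a second drug "by noncompartmental analysis of the plasma concentration-time data: AUCinf, AUClast, CL(/F), Cmax, t1/2, tlag, tmax, Vz(/F". The cell names the second drug as fluvoxamine. Section 2.13.6 (Analysis of pharmacokinetic endpoints) lists nortriptyline, morphine and M6G concentrations, so nortriptyline is the analyte meant. Table 2 does not say which parameter applies to which analyte.

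Table 1 places PK samples at pre-dose, 1, 2, 4, 5, 6, 8 and 24 h. A footnote on the 2 h and 5 h samples reads "PK sample taken 3 minutes after dosing", which makes them 2 h 03 and 5 h 03. Section 2.5.1 ends the stay there: "Subjects will be discharged in the afternoon of Day 2, approximately 24 hours post-dose". Section 2.7.1 gives morphine as a 3 mg bolus at 2 h and a 7 mg bolus at 5 h.

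On nortriptyline, section 2.2.2 states: "It exhibits a half-life of 18 to 44 hours depending on metabolic phenotype", and "with peak plasma concentrations occurring within 2 to 8 hours". On morphine, the same section gives a half-life of 15.1 h (M6G 12.9 h), clearance 1.27 L/h/kg and volume 2.9 L/kg.

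Section 2.10.4 says that deviations from the expected times "will be within ten percent, calculated from the zero point, time of drug administration". Section 2.13.6 drops a concentration from the descriptive statistics only when its time "differs from the protocol time by more than 10% and at least 5 minutes", and in general keeps it in the noncompartmental analysis. The procedure for that analysis is left to an SOP. Population PK models are optional.

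**The concern.** The endpoints, the sampling times and the half-lives all stand in this protocol, and they do not fit together. AUCinf, t1/2, CL/F and Vz/F all need a log-linear terminal slope. With one sample after 8 h and a half-life of up to 44 h, that slope depends almost wholly on two or three points spanning less than one half-life. Section 2.13.6 would still summarise each individual parameter with means and geometric CVs, and it states no limit on the extrapolated share.

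Morphine adds a second difficulty. One profile contains two doses, Table 2 gives no rule for that, and no sample is scheduled immediately before the second bolus. The sampling window also runs on the oral-dose clock, so a concentration taken before a bolus can count as the sample 3 minutes after it.

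At stake is the secondary PK objective. Half-life, clearance, volume and total exposure could be reported as measured when the design hardly informs them.

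**Working it through.** **Inputs.** Sampling and dosing times, half-lives, nortriptyline tmax, morphine CL and V, and the predicted nortriptyline exposure come from the protocol sections above. Body weight 70 kg, 10% assay and model error, and the shape of the morphine curve are assumptions. The protocol states no extrapolated share that could be reproduced.

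**1. Nortriptyline: half-lives covered.** 24/18 = 1.33 and 24/44 = 0.55.

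**2. Nortriptyline: share of AUCinf beyond 24 h.** In a one-compartment model the share is at least exp(−ln2 × 24/t½).
- t½ 18 h: exp(−0.924) = 0.397
- t½ 44 h: exp(−0.378) = 0.685

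Adding first-order absorption with tmax between 2 and 8 h raises these to 40–46% and 69–71%.

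The protocol's own prediction gives a check that needs no model: "A 75 mg oral dose is predicted to yield a peak concentration of approximately 45 ng/mL and an AUC of about 1350" ng·h/mL. Even a curve held flat at the peak for 24 h gives 24 × 45 = 1080, so at least (1350 − 1080)/1350 = 20% lies later, if the 1350 is an AUC to infinity.

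**3. Nortriptyline: how well the slope is determined.** If tmax is 8 h, only the 24 h sample follows the peak. With tmax 5 h, 10% log-normal error and a slope through 6, 8 and 24 h, simulation gives these 5th to 95th percentiles:

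| True t½ | Estimated t½ | Estimated / true AUCinf |
|---|---|---|
| 18 h | 14–28 h | 0.84–1.33 |
| 44 h | 26–183 h | 0.65–3.65 |

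CL/F and Vz/F inherit this spread.

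**4. Morphine: terminal phase.** The last sample is 24 − 5 = 19 h after the second bolus: 19/15.1 = 1.26 half-lives (M6G 19/12.9 = 1.47). In a biexponential model with the stated CL and 15.1 h, an assumed fast-phase half-life of 0.5–1.6 h and an assumed 5–30% of AUC in the slow phase, a fit to 6, 8 and 24 h returns 2.4–4.5 h. Only 2–12% of the total AUC lies beyond 24 h.

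**5. Morphine: per-dose values.** The 3 mg dose has two samples of its own, at 2 h 03 and 4 h. In the same model they return only the fast phase (0.5–1.7 h), and 6–45% of that dose's AUC falls after the 7 mg bolus. A one-compartment curve gives k = 1.27/2.9 = 0.438 per h and exp(−0.438 × 3) = 27%. Cutting the profile at 5 h therefore does not separate the doses.

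**6. Morphine: AUC if trapezoids cross the boluses.** In the one-compartment curve at 70 kg, the true AUC is 10,000/(1.27 × 70) = 112.5 ng·h/mL. Linear-up/log-down on the schedule gives 135.4, and 135.4/112.5 = 1.20. Nearly all the excess comes from two segments:
- 1 h to 2 h 03: 7.6 against a true 0.7
- 4 h to 5 h 03: 23.0 against a true 6.9

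That curve has a half-life of ln2/0.438 = 1.6 h, not 15.1 h. The biexponential curves give 1.21–1.63. The result is a range of about +20% to +63%.

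**7. Sampling window.** 10% of 123 min = 12.3 min; 10% of 303 min = 30.3 min. The 5 h 03 sample is in time from about 27 min before the bolus to 33 min after it. In the one-compartment curve, a value just before the bolus is 89% below the +3 min value (4.0 against 37.6 ng/mL), and a value at +33 min is 20% below it.

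**The case against.** The strongest reply has five parts.

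- **The list is generic.** Its notation covers oral and IV routes, and Table 2 does not claim that every parameter applies to every analyte. This is fair for M6G clearance and volume and for morphine tlag, where the remedy is clarification. It does not help nortriptyline, the only oral drug, to which CL/F and Vz/F must refer.
- **The SOP and laboratory manual are not shown.** They may contain acceptance limits and a rule for repeated doses. This stands for the morphine AUC: the protocol never says that trapezoids cross a bolus, and back-extrapolation would remove most of the bias. No SOP can supply samples after 24 h or between 8 and 24 h.
- **Bias cancels within subject.** Both periods share one schedule, so a constant bias in morphine AUC would largely cancel between treatments. This holds if nortriptyline leaves morphine kinetics unchanged. The modelled bias itself depends on the fast-phase half-life.
- **The window rule touches descriptive statistics only.** This is correct, and section 2.13.9 uses the scheduled time only when the actual time is missing.
- **PK is secondary and the study exploratory.** This limits the weight of the point but does not remove the mismatch.

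A reader might also infer that these parameters would contaminate later PK/PD modelling. The documents do not support that. Models may be developed under a separate plan, and nothing makes noncompartmental values their input.

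**Conclusion.** The point holds for a defined subset of parameters. For nortriptyline, AUCinf, t1/2, CL/F and Vz/F are not reliably estimable by noncompartmental analysis. The share of AUCinf beyond the last sample is at least 40% to 69% over the protocol's half-life range, assuming one-compartment kinetics, and only one sample may follow a late peak. For morphine, terminal t1/2, Vz and any per-dose parameter are likewise unreliable. M6G CL and Vz lack an administered dose, and morphine tlag has no meaning.

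A reader might conclude that the whole Table 2 list is out of reach. It is not. AUClast, observed Cmax and observed tmax can be had for every analyte, although for morphine the last two largely reflect the fixed 3-minute samples. A coarse tlag can be had for nortriptyline. Combined-dose morphine AUC and CL can be approximated if each bolus is treated as a new dose.

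Nor should one number be attached to morphine AUC bias. About +20% to +63% applies only if trapezoids cross the boluses, and it depends on the assumed curve.

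The window defect is real but small in reach: it affects the concentration summaries, not in general the derived parameters.

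**What to change.** - **Nortriptyline (Table 2):** correct the drug name. Report Cmax, tmax and AUC0–24. Remove AUCinf, t1/2, CL/F and Vz/F from the noncompartmental list, and take them from a population PK model if they are wanted.
- **Morphine:** report combined-dose AUC. Extrapolate the concentrations at each bolus time backward or forward from that dose's own samples, rather than interpolating across the bolus. Leave per-dose and terminal parameters to population PK. Drop tlag.
- **M6G:** drop CL and Vz.
- **Sections 2.10.4 and 2.13.6:** measure sampling-time deviations of morphine and M6G samples from the preceding bolus, not from time zero. For a 3-minute sample, 10% is 0.3 min, so the existing 5-minute floor would govern and still reach 2 min before the bolus. Add that a sample drawn before a bolus is not summarised as a post-bolus value.

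The cost is wording in the endpoint table and two sections, and fewer noncompartmental parameters in the report. No extra blood sample or visit is needed. The changes should be made before any PK data exist.

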#### 2.5 STUDY PLAN AND DESIGN

#### 2.5.1 Trial design

This is a single centre, double blind, double dummy, placebo-controlled, study to investigate the effect of morphine and nortriptyline on pain thresholds and cognitive functioning. The overview of all assessments including time schedule is provided in Table 1.

#### Screening

The Screening Visit may be conducted anytime up to 42 days prior to Baseline/admission to CHDR. The screening phase will only be started after full written, verbal and signed informed consent has been obtained, according to CHDR standard operating procedures. A full medical screening will be performed to assess a subject's eligibility for this study. The overview of the assessments of this visit is provided in the study flow chart (Table 1).

